13.0 CRITERIAFOR REMOVAL FROM STUDY

Patients will be removed from the study for any of the following reasons but they will not be replaced (see ntention to treat analysis below):

- If at any time the patient is found to be inevaluable for the protocol as designated in the section on Criteria for Patient/Subject Eligibility (e.g., a change in diagnosis), she will be removed from the study.
- If the patient decides to withdraw consent or discontinue participation in the study, she will be removed from the study; however, the Prevena will only be removed for medical reasons and not because the patient is withdrawing from the study.

The following patients will come off study, but they will be included in the analysis:

- If the Prevena Incision Management System is removed prior to 2 days after initial placement, the patient will be included in the analysis as a failure.
- If the patient experiences any grade 4 toxicity as per the MSK Secondary Surgical Events system.

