14.0 BIOSTATISTICS

An institutional database with information regarding surgical procedures performed by the GYN service at MSK was queried after the institution of a surgical site infection (SSI) reduction bundle in January 2015. Data for the period between 1/1/15 and 6/30/15 demonstrates a total of 248 laparotomies performed for all malignant indications and benign indications for patients with a BMI \geq 40 on the gyn service. 19 cases of wound complication

were noted resulting in a rate of 7.6%. We have chosen a baseline wound complication rate of 10% to take into account potentially higher rates of wound complications in alliance sites that have not yet incorporated an SSI reduction bundle.

Given our known yet unpublished rate of wound-related complications in morbidly obese patients undergoing laparotomy of 27%, it is also important to include this patient population with a clear elevated rate of wound morbidity in our study, even if it will only represent ~1% of our total cases.

With a baseline rate of 10%, we would choose a 50% decrease in the rate of complication to 5% as clinically significant. To achieve 80% power with a type I error of 10% (2 sided test), we will need to enroll a total of 686 patients. Data from our department demonstrates ~38 eligible laparotomies at MSKCC main campus per month. Over the course of the year, this would result in 456 eligible cases per year. If only 30% of eligible patients chose to enroll on study, this would result in 137 patients accruing yearly, which would require 5 years to complete the study.

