The primary objective analysis of our study will be performed via a two sample test for binomial proportions to compare the difference in proportions between the 2 arms at a type I error of 10%. We will also estimate the proportion of patients with post-op wound complication within 30 days and 90% Confidence interval for each arm assuming binomial proportions. We will perform an intent to treat (ITT) analysis where all patients who were randomized will be included in the analysis in the arm they were randomized to. If the Prevena Incision Management System is removed prior to 2 days after initial placement, the patient will be included in the analysis as per ITT and they will be considered as failures. We expect that <5% of the enrolled patients will have the Prevena system removed prior to 2 days after placement. All patients who were randomized will be evaluable for the analysis except patients that require abdominal reoperation within 30 days to address a postoperative complication unrelated to the surgical wound or patients whose BMI is less than 40 who are found to have benign pathology following their surgery. These patients will be considered non-evaluable for primary endpoint. Patients that require any surgical intervention within 30 days specifically to address a wound related complication will be considered evaluable. Patients removed from the study for reasons listed in Section 13 will be included in the analysis as per ITT principle. We will continue accrual until 686 evaluable patients are randomized.

Interim Analysis: The study will be terminated if either the futility or efficacy boundaries are crossed at the interim analysis when 343 evaluable patients have been randomized. The boundaries for the Z-test statistic after half patients (n=343) are enrolled and randomized when the interim analysis will occur are +/-0.246 for futility and +/-2.538 for efficacy. At the end of the study the boundaries will be +/-1.662.

This secondary objective analysis will analyze each type of complication separately namely wound infection, separation, and formation of seroma or hematoma, in a logistic model where the outcome is the presence and absence of wound complication and the covariate of

interest is the intervention arm (A or B). This analysis will be hypothesis generating as we expect very low rates of each one of these outcomes. P-values will not be adjusted for multiplicity.

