15.2 Randomization

Patients will be randomized (1:1) to either arm A (placement of Prevena wound vac) or arm B (standard dry gauze dressing) immediately after skin closure after all eligibility criteria are established for patients who previously consented to the study. Randomization will be accomplished by the method of random permuted block stratified by BMI > 40 (yes, no). Sealed, opaque, non-resealable envelopes containing the assignment form will be used.

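### Some patients taken off study under Section 13 are counted in the ITT analysis, but the plan does not say that their day-30 wound assessment continues or how a missing outcome is scored

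*Combined protocol and SAP*

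**What the plan says.** Section 13 (Criteria for Removal from Study) has two lists.

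- **Removed and not replaced.** This list covers consent withdrawal and late-found ineligibility: "If at any time the patient is found to be inevaluable for the protocol as designated in the section on Criteria for Patient/Subject Eligibility". A change in diagnosis is the example given. The lead-in points to the ITT analysis.
- **Off study but analysed.** The lead-in is "The following patients will come off study, but they will be included in the analysis". The first entry is Prevena removal before 2 days, which is scored as a failure. The second is "If the patient experiences any grade 4 toxicity as per the MSK Secondary Surgical Events system", with no outcome assigned.

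Section 14 (Biostatistics) states: "Patients removed from the study for reasons listed in Section 13 will be included in the analysis as per ITT principle". The same paragraph makes two groups non-evaluable for the primary endpoint: abdominal reoperation within 30 days for a complication unrelated to the wound, and benign pathology with BMI below 40. It repeats the failure rule for early device removal and continues accrual to 686 evaluable patients.

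Sections 4.1 and 10.0 define the endpoint as any wound complication up to the visit at day 30 +/- 5. Sections 4.2 and 9.0 give one explicit reason to end follow-up early, a documented wound event, when the outcome is already known. They also allow a telephone assessment if the visit cannot take place in time.

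**The concern.** Section 13 does not separate leaving the study from ending outcome assessment. Take a patient with a non-wound grade 4 event on day 5 and an intact wound. She is off study, must be analysed, and has 25 days of the endpoint window ahead of her. The plan neither tells the site to assess her at day 30 nor tells the analyst how to score her if nobody does.

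Safety reporting does not fill the gap. Section 17.2 exempts grade 1 to 4 wound seroma, hematoma, infection and separation from SAE reporting and leaves them to the study data sheets. If the sheets stop when a patient comes off study, no other study report has to carry the event.

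A pump dressing is compared with gauze, and no masking is described. Outcomes lost after a severe event, or after an eligibility judgement made with the arm known, may be lost unequally between arms. Scoring chosen at analysis would also be chosen with the data in hand.

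**Working it through.** **1. The plan's own figure.** The inputs are "With a baseline rate of 10%, we would choose a 50% decrease in the rate of complication to 5% as clinically significant" and "To achieve 80% power with a type I error of 10% (2 sided test), we will need to enroll a total of 686 patients" (Section 14), "Patients will be randomized (1:1) to either arm A" (Section 15.2) and a "two sample test for binomial proportions to compare the difference in proportions between the 2 arms at a type I error of 10"% (Section 14). With pooled variance under the null and no continuity correction:

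n per arm = [1.645 × √(2 × 0.075 × 0.925) + 0.842 × √(0.10 × 0.90 + 0.05 × 0.95)]² / 0.05² = 342.1, rounded up to 343, so 686 in total.

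The plan's figure is reproduced. Power at 343 per arm is 80.1%.

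**2. Who is in the gap.**

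| Section 13 group | In the primary analysis? | Outcome rule? |
|---|---|---|
| Grade 4, itself a wound complication | Yes | Already an event |
| Grade 4, non-wound, abdominal reoperation | Non-evaluable (Section 14) | Not needed |
| Grade 4, non-wound, no such reoperation | Yes | **None** |
| Late ineligible: BMI below 40, benign pathology | Non-evaluable in one sentence of Section 14, included per ITT in another | Conflict |
| Other late ineligible | Yes | **None** |
| Consent withdrawn | Yes | **None** |
| Prevena removed before 2 days | Yes | Failure |

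**3. Size of the gap.** The documents do not give the share m of patients with an unknown outcome, so m is an assumption here. The calculation is for a fixed design and ignores the interim look.

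Power = Φ{[Δ√n − 1.645√(2p̄(1−p̄))] / √(p₁(1−p₁) + p₂(1−p₂))}, where Δ is the difference between the arm rates and p̄ their mean.

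- Scored as non-events: each rate becomes p(1 − m).
- Dropped: n becomes 343(1 − m).
- Scored as failures: each rate becomes p(1 − m) + m.

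| m, both arms | Non-events | Dropped | Failures |
|---|---|---|---|
| 1% | 79.7% | 79.7% | 75.5% |
| 2% | 79.3% | 79.4% | 71.3% |
| 5% | 78.1% | 78.3% | 60.3% |

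Equal loss costs little power when patients are dropped or scored as non-events. The choice of scoring rule matters more than the number lost.

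**4. The early-removal rule, separately.** Section 14 expects fewer than 5% of enrolled patients to have early removal. Here a share m of the Prevena arm, assumed to have the same underlying 5% risk, is scored as failures. The Prevena rate becomes 0.05(1 − m) + m, and the control rate stays at 10%.

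| m, Prevena arm only | Prevena rate | Power in favour of Prevena |
|---|---|---|
| 1% | 5.95% | 62.3% |
| 2% | 6.90% | 42.6% |
| 5% | 0.0475 + 0.05 = 9.75% | 6.2% |

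These patients do not lack a primary outcome. They have an assigned one that need not match their wound status and that cannot arise in the gauze arm.

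**The case against.** The strongest reply is that the plan nowhere says that coming off study stops outcome collection. The day-30 visit is routine care, nursing calls and urgent-care records run alongside it, and the only stated early stop is a documented event. This is fair. A reader might infer that the outcomes will not be collected, but the text is silent rather than explicit. The silence still leaves sites without an instruction and the analyst without a scoring rule.

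A second reply is that few patients are involved. Section 15.2 randomises only after eligibility is established, most criteria are known by skin closure, wound-related grade 4 events already count, and Section 14 removes two groups. This also stands. The grading scale is in Appendix D, which is listed but not reproduced in the text reviewed, so the frequency of the remaining grade 4 events cannot be judged.

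A stronger reading is tempting: that about 17 Prevena patients (5% × 343 = 17.15) would have missing outcomes, enough to overturn a positive result. With 34 against 17 events, Z = 2.47. With five more Prevena events Z = 1.67, and with six Z = 1.52, below the final boundary of 1.662. The arithmetic is right, but the documents do not support applying it here. Those 17 are early device removals and are already counted as failures, so they cannot supply unrecorded events. Losing six events from other Prevena patients would take 6/0.05 = 120 wholly unobserved patients at the planned risk, or 6/0.20 = 30 at an assumed 20% risk, with no loss among controls.

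Nor does the plan analyse every patient it takes off study, since Section 14 makes two groups non-evaluable.

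**Conclusion.** The point holds in a limited form. For non-wound grade 4 toxicity without abdominal reoperation, and for late ineligibility outside the non-evaluable groups, the plan counts patients without saying that their 30-day wound status is obtained or how it is scored if missing. Consent withdrawals share the scoring gap. The number affected is not given and is probably small. Under the assumed equal 1% to 5% loss, power is about 78% to 80% if these patients are dropped or scored as non-events. The risk is therefore selective loss where the arm is visible, and an outcome not collected may not be recoverable at analysis.

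The failure rule for early device removal is a different problem and potentially the larger one. If 5% of the Prevena arm were affected, the planned halving of risk would almost vanish from the analysis. That result assumes the 5% applies to the Prevena arm and that removed patients carry the arm's ordinary risk. Because failure names no complication type, their component outcomes for the secondary objective could also go unrecorded.

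The documents also disagree with themselves on two points. Section 13 removals are included per ITT although some are non-evaluable, and removed patients are not replaced although accrual continues to 686 evaluable.

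**What to change.** 1. **Section 13:** state that coming off study or off device does not end the discharge/POD 7 and day-30 wound assessments, by visit or telephone, unless the patient withdraws consent for data collection. Record the date and reason for each separately. This concerns outcome collection only and leaves the rules on when the dressing is stopped untouched.
2. **Section 14, missing outcomes:** state one primary scoring rule for outcomes still missing, the same in both arms and covering consent withdrawals, with a sensitivity analysis that varies the assumption by arm.
3. **Section 14, early device removal:** analyse these patients on observed wound status and keep the failure rule as a sensitivity analysis. This replaces a prespecified scoring rule, so the amendment should say so openly and give the reason.
4. **Sections 13 and 14:** reconcile ITT inclusion and non-replacement with the two non-evaluable groups and with accrual to 686 evaluable patients.

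The cost is mainly amendment wording and a data-form field. The visit is already routine and the telephone fallback already exists. The sample size of 686 does not change.

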14.0 BIOSTATISTICS

An institutional database with information regarding surgical procedures performed by the GYN service at MSK was queried after the institution of a surgical site infection (SSI) reduction bundle in January 2015. Data for the period between 1/1/15 and 6/30/15 demonstrates a total of 248 laparotomies performed for all malignant indications and benign indications for patients with a BMI \geq 40 on the gyn service. 19 cases of wound complication

were noted resulting in a rate of 7.6%. We have chosen a baseline wound complication rate of 10% to take into account potentially higher rates of wound complications in alliance sites that have not yet incorporated an SSI reduction bundle.

Given our known yet unpublished rate of wound-related complications in morbidly obese patients undergoing laparotomy of 27%, it is also important to include this patient population with a clear elevated rate of wound morbidity in our study, even if it will only represent ~1% of our total cases.

With a baseline rate of 10%, we would choose a 50% decrease in the rate of complication to 5% as clinically significant. To achieve 80% power with a type I error of 10% (2 sided test), we will need to enroll a total of 686 patients. Data from our department demonstrates ~38 eligible laparotomies at MSKCC main campus per month. Over the course of the year, this would result in 456 eligible cases per year. If only 30% of eligible patients chose to enroll on study, this would result in 137 patients accruing yearly, which would require 5 years to complete the study.

The primary objective analysis of our study will be performed via a two sample test for binomial proportions to compare the difference in proportions between the 2 arms at a type I error of 10%. We will also estimate the proportion of patients with post-op wound complication within 30 days and 90% Confidence interval for each arm assuming binomial proportions. We will perform an intent to treat (ITT) analysis where all patients who were randomized will be included in the analysis in the arm they were randomized to. If the Prevena Incision Management System is removed prior to 2 days after initial placement, the patient will be included in the analysis as per ITT and they will be considered as failures. We expect that <5% of the enrolled patients will have the Prevena system removed prior to 2 days after placement. All patients who were randomized will be evaluable for the analysis except patients that require abdominal reoperation within 30 days to address a postoperative complication unrelated to the surgical wound or patients whose BMI is less than 40 who are found to have benign pathology following their surgery. These patients will be considered non-evaluable for primary endpoint. Patients that require any surgical intervention within 30 days specifically to address a wound related complication will be considered evaluable. Patients removed from the study for reasons listed in Section 13 will be included in the analysis as per ITT principle. We will continue accrual until 686 evaluable patients are randomized.

Interim Analysis: The study will be terminated if either the futility or efficacy boundaries are crossed at the interim analysis when 343 evaluable patients have been randomized. The boundaries for the Z-test statistic after half patients (n=343) are enrolled and randomized when the interim analysis will occur are +/-0.246 for futility and +/-2.538 for efficacy. At the end of the study the boundaries will be +/-1.662.

This secondary objective analysis will analyze each type of complication separately namely wound infection, separation, and formation of seroma or hematoma, in a logistic model where the outcome is the presence and absence of wound complication and the covariate of

interest is the intervention arm (A or B). This analysis will be hypothesis generating as we expect very low rates of each one of these outcomes. P-values will not be adjusted for multiplicity.

For the tertiary "safety" objective, we plan to report the incident of adverse events such as blistering and contact dermatitis associated for each arm separately, as defined by the CTCAE v4.0.

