dressing. The PICO system (Smith and Nephew Healthcare, Hull, United Kingdom) is a NPWT that is meant for single, short duration use. The most frequently utilized, and studied, however, is the KCI V.A.C.® negative pressure wound therapy system (KCI, San Antonio, TX). The KCI V.A.C.® is comprised of a closed, sealed system that applies wound suction through the use of an open-celled foam covered with occlusive tape. Intermittent or continuous suction is maintained through tubing that is connected from the foam to a vacuum pump. The standard rate of negative pressure is -125 mmHg. The V.A.C.® therapy platform includes a number of different products for various clinical indications. The Prevena Incision Management System (V.A.C.® Therapy, KCI USA, Inc., San Antonio, TX) is one device intended to manage the environment of clean closed surgical incisions through the removal of wound drainage and exudate via the application of NPWT. The Prevena system is applied immediately post-surgery to the clean closed incision and allowed to remain in place for 2-7 days.

We propose conducting a randomized controlled trial of post-operative wound management with use of the Prevena Incision Management System. We believe the application of a negative pressure wound therapy device placed at completion of surgery may help reduce the rate of surgical site infection and post-operative morbidity. The need for prospective data, particularly in the oncologic community, is significant, and this device can potentially have wide ranging benefits to patients. In addition, the hospital will benefit from the knowledge acquired in this study; given that Prevena Incisions Management System is costly, it should not be adopted for use if it does not prove beneficial to patients.

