In most cases, the initial contact with the prospective subject will be conducted either by the treatment team, investigator, or the research staff working in consultation with the treatment team. The recruitment process outlined presents no more than minimal risk to the privacy of the patients who are screened and minimal PHI will be maintained as part of a screening log. For these reasons, we seek a (partial) limited waiver of authorization for the purposes of (1) reviewing medical records to identify potential research subjects and obtain information

relevant to the enrollment process; (2) conversing with patients regarding possible enrollment; (3) handling PHI contained within those records and provided by the potential subjects; and (4) maintaining information in a screening log of patients approached (if applicable).

Potential study participants who meet our basic inclusion/exclusion criteria will be approached by their physician to volunteer for this study. If the patient indicates a willingness to participate, a consenting professional will explain the study in detail. Women who volunteer and sign an informed consent will then be randomized intra-operatively to either the intervention arm (in which case they will receive immediate post-operative placement of the Prevena Incision Management System) or to the non-intervention arm (in which case they will receive standard dry gauze dressing at the completion of surgery). The goal is to obtain 686 randomized patients. We expect that about 515 of these patients will recruited from MSK. The others will be recruited from the participating sites.

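### Does a 10% control rate justified by alliance sites clash with a 5-year accrual figure built from one MSK campus?

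*Combined protocol and SAP*

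**What the plan says.** All of the sample-size reasoning is in section 14.0 (Biostatistics). The MSK query found 19 complications in 248 laparotomies. The planning rate was then raised: "We have chosen a baseline wound complication rate of 10% to take into account potentially higher rates of wound complications in alliance sites". The target is 10% versus 5% with 80% power and a two-sided type I error of 10%, giving 686 patients.

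For feasibility the same section draws on one source: "Data from our department demonstrates ~38 eligible laparotomies at MSKCC main campus per month". It makes 456 eligible cases a year, supposes that only 30% enrol, and concludes that "this would result in 137 patients accruing yearly, which would require 5 years to complete the study".

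Section 7.0 (Recruitment Plan) gives the expected split between sites: "We expect that about 515 of these patients will recruited from MSK", with the rest from participating sites. Accrual ends on a count of evaluable patients: "We will continue accrual until 686 evaluable patients are randomized". There is one interim analysis at 343 evaluable patients (futility 0.246, efficacy 2.538), and "At the end of the study the boundaries will be +/-1.662".

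**The concern.** Two parts of the planning appear to assume different trials. The only reason given for moving from 7.66% to 10% is that other sites may have more complications. The 5-year timeline needs no patient from any other site. If MSK supplied everyone, the control rate would be MSK's own, and the argument for 10% would fall away. No document gives an event rate or an accrual rate for the other sites, so the reader cannot see how a pooled 10% arises.

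The stake is power. A fixed 686 yields fewer events if the true control rate is below 10%, and a real halving would be missed more often. Section 3.0 says of the device that "it should not be adopted for use if it does not prove beneficial to patients", so a false null result would have a practical consequence.

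**Working it through.** **Inputs.** From section 14.0: 19/248; 10% versus 5%; two-sided alpha 0.10; power 80%; N = 686; 38 eligible cases a month; 30% uptake; interim at 343 with boundaries 0.246 and 2.538; final boundary 1.662. From section 15.2: 1:1 allocation. From section 7.0: 515 of 686 from MSK.

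**1. The plan's sample size.** With pooled variance under the null and no continuity correction,

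n per arm = [1.645 × √(2 × 0.075 × 0.925) + 0.842 × √(0.10 × 0.90 + 0.05 × 0.95)]² / 0.05² = 342.1, rounded up to 343.

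The total is 686, which matches the plan.

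**2. The plan's accrual.** 38 × 12 = 456; 456 × 0.30 = 136.8, or 137 a year; 686/137 = 5.01 years. This also matches, with MSK main campus as the only source.

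**3. The section 7.0 split.** 686 − 515 = 171 from other sites (24.9%). At 137 a year, 515 MSK patients take 515/137 = 3.76 years, and the other sites would need 171/3.76 ≈ 45 a year over the same time. If the full 5 years is used, MSK needs only 515/5 = 103 a year, or 103/456 = 22.6% uptake.

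**4. Is 10% compatible with the MSK data?** 19/248 = 7.66%, exact 95% CI 4.7% to 11.7%. If the true rate were 10%, 19 or fewer events in 248 would occur with probability 0.129.

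**5. Other-site rate needed for a pooled 10%.** (68.6 − 515 × m)/171, where m is the MSK rate: m = 4.68% gives 26.0%; 7.66% gives 17.0%; 10% gives 10.0%; 11.71% gives 4.9%.

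**6. Power for a 50% reduction at N = 686**, by simulating the two-look design with the stated boundaries. Other-site rates are assumptions, since the documents give none; the MSK rate is held at 7.66%.

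| Site mix and assumed other-site rate | Pooled control rate | Power |
|---|---|---|
| All MSK | 7.7% | 69% |
| 515/171, others 10% | 8.2% | 72% |
| 515/171, others 12% | 8.7% | 74% |
| 515/171, others 15% | 9.5% | 77% |
| 515/171, others 17% | 10.0% | 79% |
| 515/171, others 20% | 10.7% | 82% |

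**7. A larger influence on the same power.** Section 14.0 counts removal of the device before 2 days as a failure and expects this in under 5% of enrolled patients. Only the device arm can incur it. If a fraction r of that arm fails this way, independently of complications (an assumption), its failure rate is 0.05 + 0.95r. For r = 1%, 2% and 3% that is 5.95%, 6.90% and 7.85%, and power against a 10% control rate is about 61%, 41% and 25%.

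**The case for a change.** The case for a change is fair as far as it goes. Section 14.0 calls the 5 years the time to complete the study, not the time one campus would need. The alliance sites are the only reason offered for 10%, and no weighting leads to that number. At MSK's point estimate a pooled 10% needs about 17% elsewhere, which nothing in the documents supports. One could therefore state a single site mix, add a line giving power at lower control rates, and keep accruing until 50 pooled wound complications are recorded, up to 912 patients (the single-look N for 80% power at 7.66%). In simulation that event floor gives 76% power at a 7.7% control rate and 81% at 10%, with type I error at or below 0.100 for the null rates tried.

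The quoted facts and the arithmetic stand. The remedies are weaker:

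- Stating one mix, or labelling the accrual sentence, tidies the text but alters nothing the trial does or concludes.
- A power line running from 69% to 79% would mislead unless it also said that it assumes no failures from early device removal, which move power much further (step 7).
- The event floor is a redesign. A low pooled count can mean that the device works: at 10% versus 4%, fixed-N power is already 92%, yet accrual would be extended in 39% of trials. It could add 912 − 686 = 226 patients, and its cap itself rests on an assumed 7.66% rate.

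**Conclusion.** No change is needed. The sample size and approximately 80% power are right for the assumption the plan discloses, and 10% is a defensible planning rate, inside the MSK interval. The accrual passage is conditional on low uptake and confined to one campus, so it works as a cautious feasibility check and does not contradict the multi-site split in section 7.0. All-MSK enrolment, the basis for the 69% figure, is not what the plan intends: sections 4.1, 7.0 and 17.0 all speak of, or allow for, more than MSK's own treatment, and section 7.0 names Hartford HealthCare and expects 171 patients from participating sites.

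At the intended mix, power lies between about 7 points below and 3 points above the 79% obtained at a pooled 10%. This rests on a true MSK rate of 7.66%, an exact halving, other-site rates of 10% to 20%, and no early-removal failures. The direction is uncertain also because the MSK query states neither a complication definition nor a time window, so the trial's prospective composite could run higher or lower than 7.66%. The mismatch is a missing label on a feasibility sentence, and it does not affect the design, the analysis or how the result will be read.
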